5.4.1 Causality (relatedness) Assessment

Study site investigators will assess relatedness to vaccine or study procedures (related, possibly related, unlikely related, or not related) for unsolicited AEs, SAEs and AEs of special interest. Relatedness determinations of these events will inform IRB reporting and safety monitoring (Section 5.4.3). Solicited symptoms in **Tables 8 and 9** will all be considered to be related to vaccine and causality assessment will not be done for these events. The study investigators will use their clinical judgement to make causality assessments and may consult the Expert Safety Panel or CISA Project for assistance with causality determinations. The final causality assessment decision is the responsibility of the site PI where the subject was enrolled.

5.4.2 Reporting of Adverse Events

COVID-19 vaccine administration will follow site-specific vaccine campaign administration guidelines in accordance with current recommendations from the US Food and Drug Administration and the Advisory Committee on Immunization Practices (ACIP). There are no previously published COVID-19 trials evaluating the concomitant administration of influenza vaccine; however, we do not foresee having a significant issue with serious adverse events (SAEs).

SAEs and unanticipated problems will be reported to the CDC and all participating IRBs according to institutional requirements.

Adverse events that occur in a recipient following COVID-19 vaccination should be reported to CDC's Vaccine Adverse Event Reporting System (VAERS). Vaccination providers are required by the Food and Drug Administration to report the following that occur after COVID-19 vaccination under Emergency Use Authorization:

- Vaccine administration errors
- Serious adverse events
- Cases of Multisystem Inflammatory Syndrome
- Cases of COVID-19 that result in hospitalization or death

Reporting is encouraged for any other clinically significant adverse event even if it is uncertain whether the vaccine caused the event. Information on how to submit a report to VAERS is available at <https://vaers.hhs.gov> external icon or by calling [name].

5.4.3 Safety Monitoring Plan

As a lead site, Duke will coordinate an interim safety review. This review will be performed by a panel of vaccine safety experts. Duke will provide one subject matter expert to serve on the safety panel. CDC will appoint two subject matter experts from other CISA sites that are not participating in this study. The safety experts will review SAEs and AESI and create an interim report. This review will occur once approximately 100 subjects are enrolled or at the end of the influenza season, whichever occurs first. As the Lead Site, Duke will prepare narratives of the SAEs and AESI for the safety panel. This plan is designed to monitor safety while minimizing introduction of bias into the study and minimizing burden to study investigators.

5.5 Health-Related Quality of Life (HRQOL)

5.5.1 Generic Measures of HRQOL

HRQOL assessments will be performed for persons aged ≥ 12 years at baseline and daily for 7 days following receipt of either COVID-19 vaccine plus placebo or following COVID-19 vaccine plus influenza vaccine. Assessments will include the EQ-5D-5L and the EQ-VAS.

EQ-5D-5L

The EQ-5D is a standardized, generic measure of health status that provides information on HRQOL and activities of daily living: mobility, self-care, usual activities, pain/discomfort and anxiety/depression (<http://www.euroqol.org/>)⁴⁶. In addition, the instrument contains the EQ Visual Analogue Scale (EQ-VAS) which measures the respondent's self-rated health.

The EQ-5D-5L is the new version of the EQ-5D that increases the levels of severity from three to five to significantly increase reliability and sensitivity while maintaining feasibility and reducing ceiling effects (**Appendix A**)^{47,48}. The descriptive system comprises 5 dimensions of mobility, self-care, usual activities, pain/discomfort, anxiety /depression. For each of these dimensions, there are 5 response levels: no problems, slight problems, moderate problems, severe problems, and extreme problems. The respondent is asked to indicate his/her health state by ticking in the box against the most appropriate statement in each of the 5 dimensions. This decision results in a 1-digit number expressing the level selected for that dimension. The digits for 5 dimensions can be combined in a 5-digit number describing the respondent's health state from 11111 as best health and 55555 as worst health. These numbers are converted to a Utility Index that ranges from -0.109 (worst health) to 1.000 (best health) for US specific values. The minimum clinically important difference ranges from 0.05 to 0.1 depending on health conditions being studied. The EQ-5D-5L will be used for participants 12 years of age and older. HRQOL will not be collected for participants 5-11 years of age.

EQ-VAS

The EQ-VAS records the respondent's self-rated health on a 20 cm vertical, visual analogue scale with endpoints labelled 'the best health you can imagine' (100) and 'the worst health you can imagine' (0). The respondent marks an 'X' on the scale number to indicate how their health is 'today.' The minimum clinically important difference on the VAS is 8.

The EQ-5D-5L and EQ-VAS have several advantages for use in this study. The measure is applicable to a wide range of health conditions and treatments and provide a simple descriptive profile and a single index value for health status. It has been validated in US and international populations and in adolescents and adults of all ages^{46,49,50}. The measure is useful for monitoring the health status of patient groups at different moments in time and assessing the seriousness of conditions at different moments in time. The measure is designed for self-completion by respondents. It is simple, straightforward, take only a few minutes to complete and can easily be completed by adolescents and older adults. The instrument was designed to reduce respondent burden while achieving standards of precision for purposes of group comparisons involving multiple health dimensions. It has been widely used throughout the world in many different studies, including randomized controlled clinical trials, vaccine studies, and HRQOL studies. HRQOL will not be collected for participants aged 5-11 years of age.

5.6 Biospecimens Collection & Handling

5.6.1 Serum

Blood specimens will be collected during study visits as described in Tables 5 and 6.

All blood samples (\approx 5 or 10 mL, depending upon age of the participant) will be collected into serum separator tubes and processed as follows:

- Allow blood to clot at room temperature for at least 30 minutes while standing upright in a rack.
- Centrifuge tube within 8 hours of collection at 1100 to 1300 RCF(g) for 10 minutes.
- Gently remove the vacutainer stopper avoiding serum contamination with red blood cells. Using a single-use pipette, transfer 1.0 mL aliquots of serum (top layer) into 1.0mL or 1.8 mL cryovials, up to 5 cryovials are expected for those 12 years of age and older and up to 2 cryovials are expected for those 5-11 years of age. If less than 1 mL of processed serum is collected, it is a protocol deviation
- All cryovial aliquots will be barcode labelled and contain a unique identifier via REDCap. Numbers should be placed lengthwise on the tube.
- Freeze the cryovials at -80°C in the temperature-monitored research center freezer for future shipment.
- Serum aliquots will be stored in the Duke Human Vaccine Institute Accessioning Lab, the Johns Hopkins Center for Immunization Research laboratory, and at CCHMC Schubert Research Clinic Laboratory until planned HAI analyses at which point the samples stored at JHU and Cincinnati will be shipped to Duke for planned laboratory analysis

6 LABORATORY ANALYSES

6.1 Baseline SARS-CoV-2 antibody

Serum samples obtained at the Visit 1 (prior to vaccination) will be assayed for the presence of pre-existing SARS-CoV-2 antibody using the AdviseDx SARS-CoV-2 IgG II assay and the Alinity I SARS-CoV-2 IgG assay. The AdviseDx SARS-CoV-2 IgG II assay is a chemiluminescent microparticle immunoassay intended for the qualitative and semi-quantitative detection of IgG spike antibodies to SARS-CoV-2 in human serum. The Alinity I SARS-CoV-2 IgG assay is a chemiluminescent microparticle immunoassay intended for the qualitative detection of nucleocapsid IgG antibodies to SARS-CoV-2 in human serum. All results will be interpreted as either positive or negative. A positive result on any assay will be interpreted as a positive antibody test result. The assays are intended for use as an aid in identifying individuals with an adaptive immune response to SARS-CoV-2 indicating recent or prior infection. Both assays are currently only for use under the FDA's Emergency Use Authorization.

SARS-CoV-2 antibody assays will be performed in the Immunology Virology Quality Assessment Center (IVQAC) at the DHVI. The IVQAC is a GCLP laboratory which is also accredited by CAP, CLIA and ISO-17043.

6.2 Influenza Hemagglutination Inhibition (HAI) Assay

Influenza Hemagglutination Inhibition (HAI) Assays will be performed on sera collected, contingent on additional funding. Briefly, reference wild-type, reassortant, or vaccine virus strains representative of the specific viral antigens included in the 2021-22 influenza vaccine will be used to evaluate the relative levels of all four influenza strain-specific antibodies in

participant serum samples collected pre- and 21 or 28 days post-vaccination from all study participants. To accomplish these activities, all participant samples will be interrogated for influenza antibodies against the strains of interest using the influenza hemagglutination inhibition assay (HI). This assay is considered the “gold-standard” measure by which to evaluate seroconversion/seroprotection in response to seasonal influenza vaccination. This assay will be performed in accordance with the Duke Regional Biocontainment Laboratory Virology Unit’s fully optimized and approved SOP (RVUSOP004 Influenza HI of Serum Samples). Briefly, test samples will be assayed by HAI as duplicate 2-fold dilution series starting at 1:10. Serum dilutions are then incubated with a concentration of virus verified to possess a known potential for red blood cell (RBC) agglutination. The presence of virus-specific antibodies is visualized via incubation of the virus-serum mixture with a RBC solution; the endpoint titer for a given dilution series is then expressed as the reciprocal of the final dilution in which complete HAI is observed. By convention, seronegative samples are defined as having an endpoint HAI titer < 40 and seropositive samples as having an endpoint titer of $\geq 1:40$; and seroconversion as a 4-fold change in endpoint titer relative to pre-immunization baseline or a change from <10 to $\geq 1:40$ ⁵¹.

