5. To assess the safety profiles in the simultaneous and sequential group participants by baseline COVID-19 serostatus	5a. To compare secondary outcomes 3a, 3b, 3c, and 4a according to baseline COVID-19 serostatus
6. To assess the safety profiles in the simultaneous and sequential group participants by vaccine product (Pfizer or Moderna).	6a. To compare secondary outcomes 3a, 3b, 3c, and 4a according to vaccine product (Pfizer or Moderna).
7. To assess the effect of simultaneous administration of IIV4 and COVID-19 vaccine on IIV4 immunogenicity as assessed by hemagglutination inhibition assay (HAI)	
7a. The proportion of participants in each vaccination group with a seroprotective HAI titer ($\geq 1:40$) pre- and post-IIV4 immunization for each IIV4 antigen
 
7b. The proportion of participants in each vaccination group achieving seroconversion following IIV4 (an HAI titer $\geq 1:40$ following IIV4 if the baseline titer is $< 1:10$ or a four-fold rise in HAI titer if the baseline titer is $\geq 1:10$) for each IIV4 antigen
 
7c. The geometric mean HAI titer (GMT) for each IIV4 antigen pre- and post-IIV4 in each vaccination group
 
7d. The geometric mean fold rise (GMFR) in HAI titer for each vaccination group

8. To assess serum antibody levels to SARS-CoV-2 antigens	8a. The proportion of participants in each vaccination group seropositive to SARS-CoV-2 variants tested prior to and following mRNA COVID-19 vaccine

	8b. The geometric mean ID ₅₀ and ID ₈₀ titers of neutralizing antibodies for each SARS-CoV-2 variant tested pre- and post-mRNA COVID-19 vaccine in each vaccination group
--	---

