3.2 Laboratory Studies

3.2.1 Influenza Hemagglutination Inhibition Assay

mRNA COVID-19 vaccine naïve participants will have blood draws on Day 1 (before vaccination) and Day 21 (2021-2022 season) or Day 29 (2022-2023 season) (Pfizer/BioNTech mRNA vaccine) or Day 29 (Moderna mRNA post-IIV4 vaccination to be stored for serum hemagglutination inhibition (HAI) antibody titers. Those receiving a booster dose of mRNA COVID-19 vaccine will have blood draws on Day 1 (before vaccination) and Day 29. HAI antibody titers will be compared between groups receiving COVID-19 and IIV4 simultaneously or sequentially for each of the four influenza vaccine strains contained in the respective vaccines for that season. Participants will not receive individual HAI antibody titer results; these are not routinely used in clinical practice.

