## 4 STUDY DESIGN

### 4.1 Study Description

This study is a prospective, randomized, clinical trial to assess the safety of simultaneous versus sequential administration of mRNA COVID-19 and IIV4 vaccines in 450 persons age  $\geq 5$  years enrolled at Duke University Medical Center (Lead Contractor), Johns Hopkins University (Contributing Contractor), and Cincinnati Children's Hospital Medical Center (Contributing Contractor). Participants will be enrolled in the 2021-2022 and 2022-2023 influenza seasons. Individuals will be enrolled who have not received their influenza vaccine during the influenza season during which they are recruited and are either receiving a booster dose of mRNA COVID-19 vaccine (12 years of age or older) or are receiving a primary two-dose mRNA COVID-19 vaccine series (5 years of age or older). Health, demographic and health-related quality of life (HRQOL) data will be collected from study participants at baseline for participants aged  $\geq 12$  years. All participants receiving an mRNA COVID-19 vaccine on Day 1 (Visit 1) will be randomized to receive quadrivalent inactivated influenza vaccine (IIV4) or placebo injection. Persons aged  $< 65$  years will receive standard dose IIV4 (SD-IIV4) or saline placebo injection. Children  $< 9$  years of age must only need to receive a single dose of IIV4 per ACIP recommendations for the 2022-2023 season. Persons aged  $\geq 65$  years will receive high-dose IIV4 (HD-IIV4) or saline placebo injection. Participants will receive the vaccines in an observer-blinded manner on the same day as they receive mRNA COVID-19 vaccine. Seven to fourteen days later (Visit 2) those who received IIV4 at Visit 1 will receive placebo and those who received placebo on at Visit 1 will receive IIV4 (SD-IIV4 or HD-IIV4, depending upon age). Participants will then receive a second mRNA COVID-19 vaccine (Visit 3), if applicable, and according to the recommended schedule for vaccination for the respective mRNA COVID-19 vaccine product used.

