### Major Protocol Violations for Influenza and SARS-CoV-2 Immunogenicity Analysis

1. Major Protocol Violations for Exclusion from Immunogenicity Populations:
  - a. Not all study vaccines received
  - b. No pre- and/or post-vaccination blood draw or insufficient volume for assay analysis for respective vaccine\*
  - c. Receipt of any other vaccine between the pre- and post-vaccination blood draws
  - d. New immunosuppression disorders between the pre- and post-vaccination blood draws or receipt of immunosuppressive medication between the pre- and post-vaccination blood draws
  - e. Subject who was inadvertently enrolled and randomized to the study, though they were later learned to have had met the following criteria (see f-k below) for study exclusion that would have affected immunogenicity
  - f. Influenza vaccine receipt during the current influenza season prior to study enrollment
  - g. COVID-19 vaccine prior to enrollment unless presenting for a booster dose
  - h. Prior receipt of non-mRNA COVID-19 vaccine
  - i. Use of oral or parenteral corticosteroids ( $\geq 20\text{mg/day}$  prednisone equivalent) or high-dose inhaled glucocorticoid for  $\geq 14$  consecutive days within the preceding 30 days
  - j. Has an active neoplastic disease (excluding non-melanoma skin cancer), a history of any hematologic malignancy
  - k. Has a history of receiving immunoglobulin or other blood product (with exception of Rh immunoglobulin) within the 3 months prior to study vaccination or during the study including Evushield or other COVID-19 monoclonal antibody.
  - l. Subject who was enrolled for both the 2021-22 and 2022-23 flu seasons may be included in immunogenicity for the 2021-2022 season only.

\*Blood draws will not be considered out of window as long as blood was collected within -7/+14 days of the protocol window for the respective vaccine

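### Protocol 6.2 ties HAI testing of every participant's sera to the 2021-22 vaccine strains, against two-season enrolment and the season-specific comparison in Protocol 3.2.1 and SAP 4.2.1

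*Protocol*

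**What the plan says.** Protocol 6.2 states that reference, reassortant or vaccine viruses "representative of the specific viral antigens included in the 2021-22 influenza vaccine will be used". It applies them to "participant serum samples collected pre- and 21 or 28 days post-vaccination from all study participants" and then adds that "all participant samples will be interrogated for influenza antibodies against the strains of interest". The only strains the section identifies are those of the 2021-22 vaccine.

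Enrolment covers two seasons. SAP 4.1, like Protocol 3.1, says: "Participants will be enrolled in the 2021-2022 and 2022-2023 influenza seasons". Protocol 3.2.1 gives HAI blood-draw days for both; for COVID-19-vaccine-naive Pfizer/BioNTech recipients they are "Day 21 (2021-2022 season) or Day 29 (2022-2023 season". The same section says titres will be compared between groups "for each of the four influenza vaccine strains contained in the respective vaccines for that season", and SAP 4.2.1 repeats this. The HAI endpoints in Protocol 2 and SAP 3.3 are defined by IIV4 antigen (for seroprotection, "pre- and post-IIV4 immunization for each IIV4 antigen") with no limit to one season.

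**The concern.** Exploratory objective 7 asks whether giving the two vaccines together alters the antibody response to the influenza vaccine. That requires testing each participant's sera against the antigens that participant was given. Protocol 6.2, the section a laboratory would work from, names the first season's antigens for everyone.

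For a second-season participant and a strain that changed between seasons, the before-and-after titres would then be cross-reactive titres to an antigen absent from the study vaccine. Pooled with first-season results, they would mix a response to the vaccine with something else under one strain label. A weaker measured rise in both arms would tend to narrow any difference in rise between arms, and so could obscure interference from co-administration.

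**Working it through.** The plan states no figure to reproduce, so the check is a comparison of texts followed by a statement of reach.

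**1. The texts side by side**

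| Question | Protocol 6.2 | Elsewhere |
|---|---|---|
| Which strains? | 2021-22 vaccine only | That season's vaccine (Protocol 3.2.1, SAP 4.2.1) |
| Whose sera? | Every participant's | HAI draws in both seasons (Protocol 3.2.1) |
| Seasons enrolled? | Only 2021-22 is named | 2021-22 and 2022-23 (Protocol 3.1, SAP 4.1) |
| Endpoint limited to one season? | Not stated | No: each IIV4 antigen (Protocol 2, SAP 3.3 and 8.3) |

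**2. One 2022-23 participant.** Protocol 3.2.1 and SAP 4.2.1 call for testing against the 2022-23 vaccine strains; Protocol 6.2 calls for the 2021-22 strains. Both can be obeyed only for a strain that is the same in the two vaccines.

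**3. Does another section resolve it?** None does. SAP Appendix 1, item l, says that a person enrolled in both seasons "may be included in immunogenicity for the 2021-2022 season only". It concerns only people enrolled twice and presupposes that both seasons have immunogenicity data. SAP 8.3 (EO7) works antigen by antigen without naming strains or seasons. Neither document says which section prevails.

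**4. Effect by endpoint, if 6.2 is followed and a strain changed**

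- *Seroconversion and geometric mean fold rise* measure change after vaccination. The vaccine did not contain the tested antigen, so a smaller measured rise is plausible. Its size depends on cross-reactivity, which the documents do not address.
- *Seroprotection and geometric mean titre* measure level. Exclusion 2 in Protocol 4.2 bars influenza vaccine only in the current season, so a 2022-23 participant may have had the 2021-22 vaccine a year earlier and carry high titres to its strains. The level could be higher or lower than against the participant's own vaccine strain.

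**5. Does EO7 handle two seasons?** SAP 8.3 stratifies the binary HAI comparisons by site, and its regression on log titre names no season term. SAP 7.1 lists influenza season only as a baseline descriptor. So even with the right strains tested, the SAP does not say whether titres to two different antigens in the same vaccine position are pooled.

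**6. Reach.** Let n be the number enrolled in 2022-23 and k the number of changed strains. The participant-by-strain results affected at each time point are n × k, out of 450 × 4 = 1,800 before exclusions. The documents give neither n nor k. Purely as an illustration, assume n = 225 (half of 450):

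- k = 0: 225 × 0 = 0
- k = 1: 225 × 1 = 225, and 225 / 1,800 = 12.5%
- k = 4: 225 × 4 = 900, and 900 / 1,800 = 50%

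**The case against.** The strongest reply is that the intent is plain. Protocol 3.2.1 and SAP 4.2.1 state the season-specific comparison, the endpoints are defined by vaccine antigen, and Protocol 7.1.8 leaves exploratory analyses to the SAP, whose version 1.0 is dated 3/2/2023, after enrolment for the second season was planned to begin. On this view one phrase in 6.2 was simply not updated, and no one chose to test second-season sera against first-season strains. That is probably how the text arose, and it counts against reading this as a deliberate analysis decision. It does not remove the inconsistency, because 6.2 is the current assay specification.

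Two stronger readings are tempting. A reader might infer that the laboratory plan conflicts with the statistical analysis section. It does not: Protocol 3.2.1 and SAP 4.2.1 are themselves laboratory descriptions, and EO7 is silent on strain and season. A reader might also infer that every HAI endpoint would be understated. The documents do not support that for seroprotection or geometric mean titre, because vaccination in the previous season is allowed and could raise titres to the older strains.

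It is also fair to say that EO7 sets no noninferiority margin, so dilution could not by itself yield a formal noninferiority claim, and that the harm is unproven while the strains are unlisted. Both points limit the weight of the concern without answering it.

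**Conclusion.** The inconsistency is real: as written, 6.2 would apply the wrong antigens to second-season participants for any strain that changed. The practical consequence is conditional on two things: that the laboratory follows 6.2 rather than 3.2.1, and that at least one strain differs between the seasonal vaccines. If none differs, only the wording is wrong. If one does, the 2022-23 HAI results for it would not measure response to the study vaccine. The dilution of seroconversion and fold rise is plausible rather than computed, and no direction can be given for seroprotection or geometric mean titre.

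The reach cannot be narrowed beyond 0 to 4 strains in an unstated share of 450 participants; the half-and-half split above is an assumption. A reader might infer a threat to the trial's main conclusion. There is none: the primary and secondary objectives concern reactogenicity and serious adverse events. Only exploratory objective 7 is touched, and Protocol 6.2 makes its assays dependent on further funding. The correction is worth making before the sera are tested.

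**What to change.** Amend Protocol 6.2 so that each participant's pre- and post-vaccination sera are tested against the four strains in the study influenza vaccine of that participant's enrolment season, in line with Protocol 3.2.1 and SAP 4.2.1.

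In SAP 8.3 (EO7), state that any strain that changed between seasons is analysed by season, or that season is a stratum when results are pooled: in the Mantel-Haenszel comparisons alongside site, and as a term in the log-titre regression.

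The cost is reagents for any changed strain, a short amendment and minor extra analysis. Analysing a changed strain by season also leaves fewer participants in each comparison. Protocol 5.6.1 has sera frozen at -80°C until the planned HAI analyses, so if the assays have not yet been run the change needs no new samples.
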